### 8.3.3. Analysis of Key Secondary Efficacy Endpoint

The proportion of participants who died for any cause (all-cause mortality) by Visit 11 (Day  $28 \pm 3$  days) is the key secondary endpoint.

- If a participant dies prior to Visit 11, the participant will be assigned a value of “yes” for the key secondary endpoint
- Participants having Visit 11 (either in-person or via phone call) will be assigned a value of “no” for the key secondary endpoint
- Participants having follow-up assessments on/after Day 25 and known to be alive for those assessments and for whom Visit 11 was not performed will be assigned a value of “no” for the key secondary endpoint
- Participants with early study termination (ET) for reasons other than death and prior to Visit 11 will not be included in the primary analysis.

The difference in the proportions between brexanolone and placebo will be analyzed using the SAS procedure GENMOD. In this model, the proportion will be the response variable, and the predictor variables will be treatment arm and age group ( $<70$  or  $\geq 70$  years).

Participants will be analyzed according to their actual age group, regardless of the age group used for randomization purposes. The proportion will be directly modeled using the binomial distribution with identity link. The point estimate, confidence interval, and p-value for the difference in the fitted proportions will be obtained using the “LSMEANS” statement to produce estimated treatment differences (ie, differences in proportions). The sample SAS code presented in Section 8.3.2 will be adapted for this purpose.

#### 8.3.3.1. Multiplicity Adjustment

No adjustment for multiplicity will be done.

The image consists of a series of horizontal black bars of varying lengths and positions, set against a white background. The bars are irregular in shape, with some having sharp ends and others being more rounded. They are positioned in a way that suggests they are redacting text or obscuring specific information. The overall effect is one of a heavily redacted or abstracted document.

The image consists of a series of horizontal bars, likely representing data in a histogram or a similar format. The bars are primarily black, with white segments at their right ends. The lengths of these white segments are not uniform, creating a visual effect where the bars appear to be stacked or layered. The image is set against a white background and is enclosed within a thick black border.

## 8.4. Safety Analysis

Safety and tolerability of brexanolone will be evaluated by adverse events, concomitant medication usage, changes from baseline in vital signs, [REDACTED], clinical laboratory evaluations, RASS, CAM-ICU, and 12-lead ECG. Safety data, including adverse events of special interest (AESI), will be listed by participant and summarized by treatment group. All safety summaries will be performed on the Safety Analysis Set using actual treatment received. Assessments will be mapped to windows, with the choice of the record following the same rule as described in Section 8.1.2.

The safety endpoints and variables considered in the summary tables for this study are summarized in [Table 3](#).

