#### 12.1.3. Vital Signs

Vital signs include systolic and diastolic blood pressure, heart rate, temperature, and respiratory rate (if not on mechanical ventilation) and are to be recorded for the times specified in Figure 1. Systolic and diastolic blood pressure and heart rate are to be collected supine or prone. Respiratory rate and temperature are collected once in any position.

Additionally, respiratory rate, heart rate, and blood pressure should be recorded for any participant who experiences an AESI (defined in Section 12.2.3) as soon as is feasible after the onset of the event and recorded as unscheduled on the CRF.

[REDACTED]

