#### 8.1.2. Visit Windows

Visit windows are defined in [Table 2](#). It is noted that certain specific endpoints might have slightly different analysis visit rules. If an endpoint will be analyzed using the visit windows, as specified in the corresponding sections of the applicable endpoints, all assessments within the window, regardless if the assessment is scheduled or unscheduled, will be included. A

participant's individual analysis visit window could potentially contain more than 1 visit. In the event of multiple visits falling within an analysis window, the latest data will be used.

The summary by analysis visit will use the "analyzed records" only – at most one per participant within each window. The data not flagged as the "analyzed record" will be included in listings. A visit that does not fall under any analysis window will remain in the database and will be included in the listings. The visit window does not apply to the baseline assessment.

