**Table 2: Visit Windows**

Scheduled Visit	Assessment Window	Analysis Visit Window	Study Day
V2	0 to 12h	>0 to $\leq$ 12h	1
V3	12h to 24h	>12h to $\leq$ 24h	1
V4	24h to 36h	>24h to $\leq$ 36h	2
V5	36h to 48h	>36h to $\leq$ 48h	2
V6	48h to 60h	>48h to $\leq$ 60h	3
V7	60h to 72h	>60h to $\leq$ 72h	3
Day 5 (V8)	Day 5	>72h to Day 5	3-5
Day 7 (V9)	Day 7	$\geq$ Day 6 to Day 10	6-10
Day 14 (V10)	Day 14	$\geq$ Day 11 to Day 17	11-17
Day 28 (V11)	Day 28	$\geq$ Day 25 to Day 31	25-31

Because endpoints are collected with different assessment schedules, some endpoint specific rules will be used:

- The clinical status assessed by RASS, and CAM-ICU in situations where RASS indicates appropriate subject alertness, will be administered daily and therefore will be windowed daily, from Day 1 through the end of study per-participant. If there is more than one assessment time point within the same day, the later assessment(s) will be used in the analysis.
- Hematology/Chemistry will be windowed according to the scheduled visits in the Protocol (Figure 1, page 11 – Visits 2 through 11). If there is more than one assessment within the scheduled visit, the later assessment will be used in the analysis.
- Vital signs will be windowed using the 12-hour interval as presented in [Table 2](#) above, up to Hour 72 (i.e., Visits 2 through 7). Starting from Day 5, it will be windowed daily, with the exception that Day 5 will be windowed as 72 hours –

Day 5. If there is more than one assessment within the same windowed time interval, the later assessment will be used in the analysis.

- Coagulation data is collected at Screening (Baseline), Visit 6, and Visit 9. Visit 6 will be windowed as 42 hours to 72 hours, and Visit 9 will windowed as 72 hours to Day 10.  
[REDACTED]  
[REDACTED]
- ECG is collected at Screening (Baseline), Visit 6, and Visit 10. Visit 6 will be windowed as 42 hours to 72 hours, and Visit 10 will windowed as Day 11 to Day 17.  
[REDACTED]

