**Table 4: Summary of Clinical Laboratory Analytes**

Biochemistry	Renal Panel: glucose, calcium, phosphorus, blood urea nitrogen, creatinine, sodium, potassium, chloride, bicarbonate Hepatic Panel: albumin, alanine aminotransferase, aspartate aminotransferase, total bilirubin, direct bilirubin, indirect bilirubin, alkaline phosphatase, total protein, lactate dehydrogenase, gamma glutamyl transferase, c-reactive protein
Hematology	red blood cell count, hemoglobin, hematocrit, white blood cell count (i.e., leukocytes) with differential, platelet count, erythrocyte sedimentation rate
Coagulation	Activated partial thromboplastin time, prothrombin time, and international normalized ratio (INR)

For the laboratory results that is “ $<$  or  $= x$ ”, where  $x$  is a number as collected in the data, the numeric part of the result will be used in the calculation in the summary tables. The same is true if the result is presented as below limit of quantification (BLQ) and a lower limit of quantification (LLOQ) value is provided – LLOQ value will be used for calculation in the summary tables. The actual results as collected will be presented in the listings. The analysis summary will be performed for the scheduled laboratory values only. The unscheduled laboratory values will be presented in the listings.

All statistical analyses of laboratory values will be performed using SI units. Numerical values and change from baseline values will be summarized by actual treatment group at each windowed visit. If a normal range is provided for the parameter, the out-of-range values will be flagged as low or high, where applicable, in the participant data listings. Shift tables will also be generated.

The number and percentage of participants with potentially clinically significant (PCS) values will be provided in separate listings in hematology, serum chemistry, and liver function tests. PCS values will be identified for specific laboratory parameters as outlined in [Table 5](#). The summaries will be based on all post-baseline values, including both scheduled and unscheduled data. Percentages for PCS tables will be based on the number of subjects contributing observations.

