#### 8.4.4. Vital Signs

Vital signs include systolic and diastolic blood pressure, heart rate, temperature, and respiratory rate (if not on mechanical ventilation). Systolic and diastolic blood pressure and heart rate are to be collected supine or prone. Respiratory rate and temperature are collected once in any position. Descriptive summaries of observed values and changes from baseline will be provided for vital sign parameters - by windowed visit and treatment group.

Additionally, the number and percentage of participants with PCS and PCS values will be summarized. PCS values will be identified for vital sign parameters as outlined in [Table 6](#).

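### SAP 8.4.4 and 8.4.5 do not say which records feed the vital-sign and ECG outlier counts, and the SAP's latest-record default would leave some unscheduled readings out of them

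*SAP*

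**What the plan says.** **General default.** SAP 8.4, after assigning all safety summaries to the Safety Set, states: "Assessments will be mapped to windows, with the choice of the record following the same rule as described in Section 8.1.2".

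**The rule referred to.** SAP 8.1.2 admits scheduled and unscheduled assessments to a window and then chooses one: "In the event of multiple visits falling within an analysis window, the latest data will be used". Summaries by analysis visit use "at most one per participant within each window". Records that are not chosen, or that fall in no window, appear in listings. The section opens its rule with a condition: "If an endpoint will be analyzed using the visit windows, as specified in the corresponding sections of the applicable endpoints".

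**Endpoint-specific windows (under SAP Table 2).** Vital signs use 12-hour windows to Hour 72, one window from Hour 72 to Day 5, and daily windows after that; the later reading in a window is the one analysed. For ECG: "Visit 6 will be windowed as 42 hours to 72 hours, and Visit 10 will windowed as Day 11 to Day 17".

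**Outlier counts.**
- Laboratory (SAP 8.4.3): "The summaries will be based on all post-baseline values, including both scheduled and unscheduled data".
- Vital signs (SAP 8.4.4): "the number and percentage of participants with PCS and PCS values will be summarized". The repeated abbreviation is presumably a slip for PCS and PCSC, since Table 6 has criteria for both. No record basis is given.
- ECG (SAP 8.4.5): PCS and PCSC counts from Table 7, plus a summary of the maximum QTcF. No record basis is given for either.

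**Readings at events.** Protocol 12.1.3 asks for respiratory rate, heart rate and blood pressure when a participant has an AESI, "as soon as is feasible after the onset of the event and recorded as unscheduled on the CRF".

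**The concern.** A latest-record rule suits a by-visit mean, where each participant should contribute once. It does not suit a count of participants who ever crossed a threshold, because that count exists to pick up extreme values wherever they occur. The SAP makes this distinction for laboratory values and does not repeat it for vital signs or ECG.

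The readings at risk are not routine ones. The protocol asks for them because an event has occurred, and records them as unscheduled. If the general default governs the counts, whether such a reading is counted depends on whether another reading happened to follow it in the same window. If the default does not govern them, the SAP gives no basis at all, and two programmers could produce different tables from the same data.

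**Working it through.** The plan states no figure on this point, so there is none to reproduce. The check is a reading of the rules, followed by tracing records through them.

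**1. Which rule reaches which display**

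| Data | By-visit summaries | PCS/PCSC counts |
|---|---|---|
| Laboratory (8.4.3) | Windowed, scheduled values only | All post-baseline values, scheduled and unscheduled |
| Vital signs (8.4.4) | Windowed, latest record | Not stated; 8.4 default is the only general rule |
| ECG (8.4.5) | Windowed, latest record | Not stated; 8.4 default is the only general rule |
| Maximum QTcF (8.4.5) | Not applicable | Not stated |

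**2. Vital signs under the default**

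- To Hour 72 there are 72/12 = 6 windows, so at most 6 analysed records per participant over that period.
- Take two readings in one window at times t1 < t2: an AESI reading at t1 with systolic pressure below the Table 6 limit of 90 mmHg, and a later reading at t2 inside the limits.
- The analysed record is the one at t2. The reading at t1 is only listed.
- The participant is then missing from the low-systolic count, unless an analysed record in another window also crosses the limit.
- If the AESI reading is itself the latest in its window, it is kept. Being unscheduled does not exclude it.
- Heart rate and systolic and diastolic pressure have Table 6 criteria. Respiratory rate has none, so it cannot enter these counts under any record rule.

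**3. ECG under the default**

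The endpoint-specific windows replace the general ones in Table 2:

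| Time of ECG | Window |
|---|---|
| Before Hour 42 | None |
| Hour 42 to Hour 72 | Visit 6 |
| After Hour 72 to Day 10 | None |
| Day 11 to Day 17 | Visit 10 |
| After Day 17 | None |

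SAP 8.1.2 says ECGs are collected at screening, Visit 6 and Visit 10, and Protocol 12.1.5 refers to scheduled time points. The gaps therefore affect unscheduled ECGs. With two post-baseline windows and one record in each, a maximum QTcF restricted to analysed records would be the larger of at most two values.

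**4. Direction**

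The analysed records are a subset of all post-baseline records. For any threshold, the participants with at least one crossing among analysed records are therefore a subset of those with at least one crossing overall:

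count (latest record per window) ≤ count (all post-baseline records)

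The inequality is strict only if some participant's crossings all lie in displaced or out-of-window records.

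**5. Size**

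The size depends on how many AESIs occur, when readings follow them, how many unscheduled ECGs are taken, and whether abnormal values recur in analysed records. The documents give none of these. The schedule figure is not shown, and its note on AESIs during infusion is cut short in the available text.

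**The case against.** The best case for the plan is that the SAP does not tie the outlier counts to windows. Section 8.1.2 makes windowing depend on the endpoint's own section, and its one-record sentence concerns summaries by analysis visit. Sections 8.4.4 and 8.4.5 mention windowed visits for the descriptive summaries and then introduce the counts in separate sentences without a window. A participant-level count over all post-baseline records is a natural reading. The laboratory contrast is also weaker than it looks: 8.4.3 first confines laboratory summaries to scheduled values, so it needed an express sentence to lift that limit for PCS counts.

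This stands in part. It defeats the stronger reading that the SAP orders these counts to be made on last records only; no sentence says so. It does not remove the problem. The 8.4 default has no exception for outlier counts, the vital-sign rule under Table 2 says without qualification that the later reading is the one analysed, and nothing in 8.4.4 or 8.4.5 overrides either.

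A reader might infer other things that the documents do not support:

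- **That 70% of ECG data are lost.** No window covers 42 of the 60 planned infusion hours (42/60 = 70%), but that is clock time. No ECG is scheduled between baseline and Visit 6, and Protocol 12.1.3 orders vital signs, not an ECG, at an AESI.
- **That half or more of AESI readings are lost.** If the AESI reading and m others fell at independent uniform times in one window, it would be displaced with probability m/(m+1): 50% for m = 1, 67% for m = 2, 75% for m = 3. Those times are assumed. Displacing a reading is also not the same as missing a participant.
- **That the events vanish from the safety tables.** AESIs are tabulated under SAP 8.4.1. Vital-sign and ECG changes that meet the criteria in Protocol 12.2.1 are adverse events and enter those tables. Every record stays in the listings. The adverse-event route does not fully replace the counts, because it depends largely on intervention or clinical judgement, whereas the counts apply fixed thresholds.
- **That later readings are systematically the recovered ones.** This is plausible for transient events, but nothing in the documents establishes it. The defined AESIs are reintubation, delirium, sedation, altered mental status and loss of consciousness, not haemodynamic events.

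**Conclusion.** The point holds as a gap with an unsuitable default. The SAP sets a latest-record rule for safety assessments, exempts only laboratory PCS counts expressly, and leaves the record basis of the vital-sign and ECG PCS/PCSC counts and the maximum QTcF unstated. If the default is followed, some event-triggered heart-rate and blood-pressure readings and some unscheduled ECGs are left out of those counts. The effect can only be downward or nil, and its size cannot be determined from the documents.

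The conclusion assumes that a programmer who finds no rule in 8.4.4 or 8.4.5 would turn to 8.4. If an all-records reading were used instead, the counts would be sound but the SAP would still not say so.

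Severity is minor. These are descriptive tables, no endpoint test or stopping rule depends on them, and the underlying events remain visible elsewhere. The point goes beyond missing detail because the stated default is the wrong kind of rule for a worst-value count.

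**What to change.** Add one sentence to SAP 8.4.4 and one to SAP 8.4.5, stating that PCS and PCSC counts, and in 8.4.5 the maximum QTcF, use all post-baseline records, scheduled and unscheduled, whether or not they fall in an analysis window. This is the basis that 8.4.3 already uses for laboratory PCS values. State that the one-record-per-window rule applies to by-visit descriptive summaries only. In the same edit, correct the repeated abbreviation in 8.4.4 if PCSC was meant.

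The cost is two sentences and the matching change to the programming specifications. No new data are needed, because unscheduled readings are already recorded and listed. The change belongs before database lock; under SAP Section 2, a later change would have to be documented in the clinical study report.

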**Table 3: Safety Endpoints and Variables in the Summary Tables**

Safety Evaluation	Incidence	Raw Value	Change from Baseline	Normal Range Shift from Baseline	Potentially Clinically Significant (PCS)	Abnormality/ Clinical Significance
AEs	X					
Labs		X	X	X	X	*
ECG		X	X		X	*
Vital Signs		X	X		X	
<define all abbreviations and shorthand (eg, “labs”) used in the table> X = Safety Assessment will be summarized in tables * = Safety Assessment will be summarized in individual participant data listings						

#### 8.4.1. Adverse Events

Adverse events will be coded using Medical Dictionary for Regulatory Activities (MedDRA) Version 23.0 or higher. A treatment-emergent adverse event (TEAE) is defined as an adverse event with onset after the initiation of IP. The analysis of adverse events will be based on the concept of TEAEs.

If the date of an adverse event is incomplete and an unambiguous determination could not be made with respect to its onset time versus the first dose of IP and/or last dose of IP, the adverse event will be assumed to be a TEAE and a treatment period TEAE. For imputation of missing AE dates, please refer to Appendix A.

The incidence of all TEAEs and non-serious TEAE's will be separately summarized by SOC and preferred term PT. In addition, summaries will be provided by maximum severity (mild, moderate, severe, life-threatening, death) and by relationship (related, not related) to IP. Any TEAEs leading to discontinuation of treatment or withdrawal from the study and any treatment-emergent serious adverse events will also be summarized, sorted by descending frequency in SOC and PT.

For maximum severity, participants will be counted only once within each SOC and PT at the maximum severity in the following order: severe > moderate > mild; an AE with missing severity will be omitted from severity presentation. A participant will be counted only once within each SOC and PT at the strongest relationship to IP in the following order: related > not related. The incidences will be presented by descending frequency of SOC in the brexanolone group and then, within a SOC, by descending frequency of PT based on the participant count, and in alphabetical order of PT if the incidence within a PT is a tie.

The following table documents events considered to be AESI in this study, and the MedDRA preferred terms and lower-level terms (i.e., LLTs) in the right-hand column will be used to screen adverse events for possible AESI status. Where LLTs are specified, they take precedence in the determination of AESI's; when LLTs are left unspecified, it is understood that MedDRA preferred terms will take precedence:

AESI Term	MedDRA Preferred Term(s)
Loss of Consciousness	
 
1. Loss of consciousness
 
2. Altered state of consciousness
 
3. Syncope
 

Excessive sedation	
 
1. Sedation
 
2. Somnolence
 
3. Sedation complication (note: this corresponds to the LLT of “Sedation excessive”)
 

Reintubation events	
 
1. Endotracheal intubation (note: this corresponds to the LLT of “Reintubate”)
 
2. Endotracheal intubation complication (note: this corresponds to the LLT of “endotracheal reintubation”)
 

Delirium	
 
1. Delirium
 
2. Intensive care unit delirium
 
3. Anesthetic complication neurological (note: this corresponds to the LLT of “Delirium on emergence”)
 

Altered mental status	
 
1. Mental status changes (note: this corresponds to the LLTs of “Acute mental status changes” and “Mental status changes”)
 
2. Mini mental status examination abnormal
 

The process for identification of AESI is to screen for MedDRA terms in the right-hand column and to query once any adverse events have been identified as meeting these broad criteria. AESI's will be tabulated separately from all TEAE's, using the same SOC x PT format.

All AEs, AESI and SAEs (including those with onset or worsening before the start of IP) through the end of the study will be listed. In addition, a listing containing individual participant's AE data for participants who died, and participants with SAEs leading to treatment discontinuation will be provided, separately.

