### 12.2.1. Adverse Event Definition

An AE is any untoward medical occurrence in a patient or clinical investigation participant administered a pharmaceutical product and that does not necessarily have a causal relationship with this treatment. An AE can therefore be any unfavorable and unintended sign (including an abnormal laboratory finding), symptom or disease temporally associated with the use of a medicinal (investigational) product whether or not related to the medicinal (investigational) product. In clinical studies, an AE can include an undesirable medical condition occurring at any time, including baseline or washout periods, even if no study treatment has been administered.

A TEAE is defined as an adverse event with onset after the start of IP, or any worsening of a pre-existing medical condition/adverse event with onset after the start of IP and throughout the study. The term IP includes any Sage IP, a comparator, or a placebo administered in a clinical trial.

Laboratory abnormalities and changes from baseline in vital signs, and ECGs are considered AEs if they result in discontinuation or interruption of study treatment, require therapeutic medical intervention, meet protocol specific criteria (if applicable) or if the investigator considers them to be clinically significant. Any abnormalities that meet the criteria for an SAE should be reported in an expedited manner. Laboratory abnormalities and changes from baseline in vital signs and ECGs that are clearly attributable to another AE do not require discrete reporting (eg, electrolyte disturbances in the context of dehydration, chemistry and hematologic disturbances in the context of sepsis).

Participants who discontinue the IP due to an AE, regardless of investigator-determined causality, should be followed until the event is resolved, considered stable, or the investigator determines the event is no longer clinically significant. Any AEs that are unresolved at the participant's last AE assessment in the study are followed up by the investigator for as long as medically indicated, but without further recording in the CRF. The sponsor or its representative retains the right to request additional information for any participant with ongoing AE(s)/SAE(s)/AESIs at the end of the study, if judged necessary.

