#### 13.6.1. Adverse Events

AEs will be coded using Medical Dictionary for Regulatory Activities (MedDRA) Version 23.0 or higher. A treatment-emergent adverse event (TEAE) is defined as an AE with onset after the start of IP. The analysis of AEs will be based on the concept of TEAEs. The incidence of TEAEs will be summarized by System Organ Class and preferred term. In addition, summaries will be provided for TEAEs Grade 3 and above per CTCAE guidelines and by causality (related, not related) to IP.

Any TEAEs leading to IP discontinuation, dose reduction, or study withdrawal and any treatment-emergent SAEs and AESIs will be summarized.

All AEs, SAEs, and AESIs (including those with onset or worsening before the start of IP) through the end of the study will be listed.

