## 6. MODIFICATIONS

### 6.1. Modifications from the Approved Clinical Study Protocol

The modifications presented in this section are intended to either clarify some aspects of the Protocol-specified analyses, modify them, or drop them entirely.

The Sponsor decided to terminate the study early due to a very challenging patient recruitment environment – the majority of residents in North America have now been vaccinated against n-Cov-19. This decision was not due to DMC recommendation and not due to safety reasons.

Modifications were made to both the overall concomitant medication analysis and the Midazolam/Propofol analysis to accommodate the nature of the collected data. Due to Sponsor decision to terminate the study early some analyses were dropped for simplicity and/or untenability (Kaplan-Meier analysis of all-cause mortality, tipping point analysis, interim analysis).

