## **11. LIST OF APPENDICES**

## APPENDIX A. HANDLING OF MISSING DATES

Dates missing the day or both the day and month of the year will adhere to the following conventions in order to classify TEAEs and to classify prior and concomitant medications.

In general, listings will present the actual partial or missing values rather than the imputed values that may be used in derivation. In instances where imputed values will be presented, imputed values will be flagged.

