### Adverse Events

If the AE start date is completely missing, do not impute a date but consider it as TEAE, unless the AE end date is before the initiation of treatment, in which case the AE will be considered prior.

For partial AE start dates:

- When the year is known, but the month and day is unknown, then:
  - If the year matches the year of initiation of study drug and the end date (if present) is after the initiation of study drug, or AE is ongoing, then impute as the month and day of the initiation of the study drug date + 1 day.
  - If the year of AE onset < year of initiation of the treatment, then the month and day will be set to December 31st.
  - If the year of AE onset > the year of initiation of treatment, then the month and day will be set to January 1st.
- If the year and month are known, but the day is unknown, then:
  - If the year of AE onset = the year of initiation of the treatment and:
    - the month of AE onset = the month of initiation of the treatment, then the day will be set to the day of initiation of the treatment.
    - the month of AE onset < the month of initiation of the treatment, then the day will be set to the last day of month.
    - if the month of AE onset > the month of initiation of the treatment, then the day will be set to the 1st day of month.
  - If the year of AE onset < the year of initiation of the treatment, then the day will be set to the last day of month.
  - If the year of AE onset > the year of initiation of the treatment, then the day will be set to the 1st day of month.

If the imputed AE onset date is after the AE stop date, then the onset date will be set to the stop date.

- When the year and day are present and the month is missing, treat it as if the day is missing, and only year is present. Follow the imputation rules for “year is known, but the month and day is unknown”.
- When the year is missing, but the month and/or day is known, treat this date as missing; do not impute.

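### The protocol defines a treatment-emergent AE in two ways, and SAP 8.4.1 carries over the one that leaves out worsening after the start of IP

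*SAP*

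**What the plan says.** Three passages define a TEAE.

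- Protocol 12.2.1 (Adverse Event Definition) gives two routes. One is onset after IP has started. The other is "or any worsening of a pre-existing medical condition/adverse event with onset after the start of IP and throughout the study".
- Protocol 13.6.1 (Adverse Events, in the statistics chapter) gives one route: "A treatment-emergent adverse event (TEAE) is defined as an AE with onset after the start of IP".
- SAP 8.4.1 repeats 13.6.1 almost exactly: "A treatment-emergent adverse event (TEAE) is defined as an adverse event with onset after the initiation of IP". It then bases the whole AE analysis on TEAEs.

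The listing sentence in both Protocol 13.6.1 and SAP 8.4.1 covers every AE, "including those with onset or worsening before the start of IP". SAP Appendix A sets its date conventions "in order to classify TEAEs and to classify prior and concomitant medications"; for AEs these work on start and end dates, with no rule for a date of worsening. SAP 6.1 describes its purpose this way: "The modifications presented in this section are intended to either clarify some aspects of the Protocol-specified analyses, modify them, or drop them entirely". Its visible items are 6.1.1, 6.1.2, 6.1.4, 6.1.5 and 6.1.6, and none concerns TEAEs. Two further items are redacted.

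TEAE incidence is listed as a secondary endpoint in Protocol 6.2.2.

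**The concern.** These participants are ventilated, or about to be, when consent is signed, so AEs that start before the infusion and are still running when it begins are to be expected. An event already present that becomes more severe on IP is one a safety table should show. It happens after randomization, and the drug could influence it. Under the 12.2.1 definition it is counted. Under the 13.6.1 and SAP 8.4.1 definition, read literally, it is not.

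If so, the event drops out of the TEAE incidence table, the severity and relationship summaries, and the treatment-emergent SAE table. Reported incidence for a named secondary endpoint would then depend on which definition the programmer follows and on how each site recorded a worsening. The plan settles neither.

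**Working it through.** No planned figure is at issue, so the check is mainly a comparison of texts.

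**1. How each text classifies the same event**

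| AE record | Protocol 12.2.1 | Protocol 13.6.1 and SAP 8.4.1 |
|---|---|---|
| Onset after IP start | TEAE | TEAE |
| Onset before IP, no change afterwards | Not a TEAE | Not a TEAE |
| Onset before IP, one record, worsens on IP | TEAE | Not a TEAE |
| Onset before IP, worsening entered as a new AE dated after IP start | TEAE | TEAE |
| Medical-history condition with no earlier AE record, worsens on IP | TEAE | Normally a TEAE, since the AE's own onset falls after IP start |

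Only the third row differs.

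**2. Does onset already include worsening?** The listing sentence names the two separately, which suggests that these sections treat them as different things. Appendix A gives no way to date a worsening. A programmer working from the SAP would compare the AE start date with the IP start and go no further.

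**3. The window for a third-row event.** Randomization must fall within 48 hours of consent (Protocol 9.5), and infusion must start within 6 hours of randomization (Protocol 10.5). 48 + 6 = 54 hours at most. SAEs are recorded from consent (Protocol 12.2.2), and AEs with onset before IP are listed, so such records can exist.

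**4. Internal consistency of the SAP.** When timing cannot be settled, "the adverse event will be assumed to be a TEAE and a treatment period TEAE". Appendix A agrees: "If the AE start date is completely missing, do not impute a date but consider it as TEAE", unless the end date falls before treatment. So an event of unknown timing is counted, while one known to have worsened on IP is not.

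**5. Size per affected participant.** If a participant has no other record under that preferred term, leaving the event out lowers that arm's incidence in that row by 1/n.

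- Planned size: about 100 participants at 1:1 gives n = 50; 1/50 = 2.0 percentage points.
- Planned interim size: n = 25; 1/25 = 4.0 percentage points.

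The final number per arm is not given. The study is ending early and the interim analysis was cancelled, so 25 to 50 per arm is an assumed range. With fewer than 25 the step would be larger.

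**6. Number of events.** This cannot be computed. The documents give no AE counts, no frequency of worsening, and no instruction on whether a worsening opens a new AE record. Protocol 12.2.5 has sites report onset, resolution, intensity and seriousness for each AE. The visible text asks for no date of grade change.

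**The case against.** The strongest reply is that the SAP narrows nothing. It matches the protocol's own statistics section, and the two analysis texts agree. **That stands.** A reader might infer that the SAP departed from the protocol without declaring it, but the documents do not support this. SAP 8.4.1 is narrower only than 12.2.1, a definitions section, and the absence of an item in SAP 6.1 proves little when two items there are redacted.

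A second reply is that the texts can be read together. The worsening limb of 12.2.1 can be taken to give the worsening an onset of its own, so an onset rule would already capture it. That is possible, but the text does not secure it. The listing sentence keeps onset and worsening apart, and no visible recording rule tells sites to open a new AE.

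A third reply is that the exposed group is small: an AE must begin within about 54 hours, continue, worsen, stay as one record, and have no companion record under the same term. **That also stands**, and nothing shows that even one such event occurred. The 2.0 and 4.0 point figures describe any single reclassified participant and do not measure a known loss.

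Nor does the event vanish. All AEs are listed, and deaths are analysed in all-cause mortality.

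A related inference would be that sedatives already running at IP start are lost from the medication summaries. SAP 8.4.2 does limit the table for CNS depressants, sedatives and delirium drugs to those started on or after IP initiation and during an ICU stay, while SAP 8.2.6 describes a class table without that limit. But 8.4.2 states the filter openly, and running drugs remain in the standard ATC Level 3 table and the concomitant medication listing. This is a labelling matter only.

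**Conclusion.** The point holds as a conflict between Protocol 12.2.1 and Protocol 13.6.1 that SAP 8.4.1 inherits in its narrower form. It should be fixed because it affects what is counted in a secondary endpoint, because the literal reading drops events known to have worsened on IP while keeping events of unknown timing, and because the remedy is cheap.

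The effect on results is unknown and may be zero. It is zero if every worsening was entered as a new AE. Otherwise, each affected participant with no other record under the term moves one row of one arm by 2.0 to 4.0 percentage points, on the assumption of 25 to 50 per arm. A reader might conclude that TEAE incidence will be understated. The documents show only that it could be, because they do not say how worsening was recorded.

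**What to change.** Before database lock:

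1. Put the Protocol 12.2.1 definition in SAP 8.4.1, and add an item to SAP 6.1 saying that it replaces the wording of Protocol 13.6.1.
2. In a blinded review of AEs ongoing at IP start, flag as TEAEs those whose recorded CTCAE grade rose, or that became serious, after IP start.
3. Where the timing of the worsening was not recorded, apply the existing SAP 8.4.1 assumption for ambiguous dates (count as a TEAE) and footnote those cases.
4. Minor: title the SAP 8.4.2 class table as new starts during an ICU stay, and cross-reference SAP 8.2.6 and 6.1.2.

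The cost is a few SAP sentences, one SAP 6.1 item, a table title and a small blinded review. TEAE counts may rise slightly, and a few worsenings that in fact came before IP may be counted under step 3. A small number of site queries may be needed, because the visible text does not show that dates of worsening were collected.
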